2.8 Outcomes Assessment Schedule

		sample collection and CRF completion									
		Baseline	1 month	1 year	2 years	3 years	4 years	5 years	6 years	7 years	8 years
CRFs	Randomisation form	✓									
	Patient history	✓									✓
	Food diary	✓									✓
	Quality of Life	✓			✓		✓		✓		✓
	Family history	✓									
	Endoscopy form	✓			✓		✓		✓		✓
	Biopsy sampling form	✓			✓		✓		✓		✓
	Pathology form	✓			✓		✓		✓		✓
	1 month fu form		✓								
	Follow-up form			✓	✓	✓	✓	✓	✓	✓	✓
	End of treatment form										✓
Sample collection ¹	Endoscopy	✓			✓		✓		✓		✓
	Biopsy samples	✓			✓		✓		✓		✓
	Blood samples	✓									✓

Notes: Food Diary, quality of life and family history only collected for first 1000 patients
In later versions endoscopy and pathology form combined

¹ Endoscopy, biopsy and blood samples collected 2 years from previous endoscopy for retrospective patients

3. QC during trial

The quality and completeness of the data will be the responsibility of the data team during the trial. The statistician will feed back any concerns of a specific or general nature to the data team.

1 year into the trial (September 2006), the integrity of the randomization was assessed. The completeness of the data is assessed at each data lock, discussed between the data team and statistician and any necessary action taken.

4. Data Monitoring Committee and Interim Analyses

The DMC met annually to monitor recruitment to the trial and protocol compliance as well as toxicity and serious adverse events. See Charter for full details.

The primary aim was analysed and presented confidentially to the DSMC after 2 years and 4 years of follow-up (interim analyses) and was reported considering a p value of 0.001 as significant. The DSMC were happy for the trial to continue and neither interim analysis was disseminated further.

5. Data Validation

It is expected that much of the data cleaning will be done by the data team. However, before analysis, all fields will be summarised and any possible fields cross referenced. This will improve understanding of the data and allow for feedback of unexpected data to the data team for clarification/correction.

Oesophagectomy, ablation therapy and endoscopic mucosal resection are commonly carried out when high grade dysplasia or oesophageal adenocarcinoma is found. All cases where this treatment is carried out without logging a disease progression will be checked.

The primary analysis and first 2 secondaries will be independently analysed by a second statistician.

AspECT

A phase III randomised study of Aspirin and Esomeprazole chemoprevention in Barrett's metaplasia

[figure not shown]
Funded by CR-UK, MRC, UHL and NCI

ISRCTN No.85156844

6. Descriptive Analyses

A descriptive analysis will be carried out first examining the study sample.

6.1 Representativeness of Study Sample and Patient Throughput

AspECT

A phase III randomised study of Aspirin and Esomeprazole chemoprevention in Barrett's metaplasia

Funded by CR-UK, MRC, UHL and NCI

ISRCTN No.85156844

The above diagram was completed for each interim analysis (2 years and 4 years after final recruitment) and will also be completed at the final analyses. Any randomised but ineligible patients will be described. These patients are included in the ITT analysis

The sensitivity analysis will use a per protocol sample of patients given a 'therapeutic' amount of treatment. See section 7 and appendix 1 for a definition of the therapeutic dose.

6.2 Baseline Comparability of Randomised Groups

A table of baseline data for all patients, each of the four intervention groups and the groups for the main comparisons will be given. This will include

Variable at baseline	Low PPI no aspirin	Low PPI and aspirin	High PPI no aspirin	High PPI and aspirin	TOTAL
Length of Barrett's metaplasia at rand (strata for minimisation and median(range), cm)					
Age (strata for minimisation, median(range), years)					
Gender Male Female					
Intestinal metaplasia Yes No					
Retrospective patient Yes No					
Duration of Barrett's pre randomisation Median (range), years					
Alcohol use None some					

AspECT

A phase III randomised study of Aspirin and Esomeprazole chemoprevention in Barrett's metaplasia

Funded by CR-UK, MRC, UHL and NCI

ISRCTN No.85156844

Variable at baseline	Low PPI no aspirin	Low PPI and aspirin	High PPI no aspirin	High PPI and aspirin	TOTAL
(For some group, median(iq range),units per week)					
Smoker No never Ex Yes current					
Myocardial Infarction Yes No					
Angina Yes No					
Coronary Intervention Yes No					
Stenosis Yes No					
Cardiac catheterisation Yes No					
Cerebrovascular Yes No					
TIA Yes No					
Peripheral Vascular Disease Yes No					
Diabetes Yes No					

AspECT

A phase III randomised study of Aspirin and Esomeprazole chemoprevention in Barrett's metaplasia

Funded by CR-UK, MRC, UHL and NCI

ISRCTN No.85156844

Variable at baseline	Low PPI no aspirin	Low PPI and aspirin	High PPI no aspirin	High PPI and aspirin	TOTAL
Hypertension Yes No					
Hyperlipidaemia Yes No					

This table will be repeated with columns of no aspirin, aspirin, low PPI and high PPI. Those taking part in the PPI only randomisation will not appear in the no aspirin/aspirin columns since they did not take part in the aspirin randomisation.

Numbers (with percentages) for binary and categorical variables and means (and standard deviations), or medians (with range) for continuous variables will be presented. There will be no tests of statistical significance nor confidence intervals for differences between randomised groups on any baseline variable.

6.3 Comparison of Losses to Follow-up

The numbers and distribution of losses to follow-up (defaulters and withdrawals) over the period of the study will be reported overall, for the four randomisation groups and for the primary objective comparison groups. Defaulters are those who attend no further trial related visits.

Note that for conversion to cancer and death from any cause, the NHS digital flagging may still be possible for those lost to active follow-up.

For other endpoints, the baseline characteristics of those lost to follow-up and between those to be analysed will be compared between the two treatment groups. Those randomised may be balanced, but those with data to analyse on the secondary objectives may not be. The consequences of this examination of the data will be described separately for each objective.

6.4 Description of Compliance with Therapy

A summary of the treatment received will be provided. This will include the dosage of drugs in each of the four treatment intervention groups and details of numbers complying with treatment. Note that compliance is assumed when a prescription is collected and patient attends trial visits.

6.5 Reliability of data

Survival time will be calculated from date of randomisation to the first of

- date of Barrett's adenocarcinoma
- date of high grade dysplasia
- date of death from any cause

with a censor variable created coded 1 for an event. If none of the above exist for a patient the survival time will be calculated from date of randomisation to

- date of last follow-up

with the censor variable coded 0 to indicate the time does not relate to an event.

This may be done using difference in defined dates in STATA (or similar function/software available at the time of analysis). A random 20 patient manual check will be done to confirm the programming of the calculation.

Other derived variables will have a 20 patient check.

6.6 Description of Available Data

Primary endpoint – survival until adenocarcinoma, high grade dysplasia or death from any cause

There will be a time for every patient. For some of the patients who do not reach an endpoint, the survival time will be less than the trial duration due to loss to follow-up. The endpoint of death and diagnosis of Barrett's adenocarcinoma can be picked up in many cases from NHS digital but the endpoint of high grade dysplasia will be under represented due to those lost to follow-up.

The median follow-up will be described using the median of those without an event and the median using the reverse Kaplan-Meier method.

Kaplan-Meier curves will be drawn for all patients, then split by aspirin intervention and split by PPI dose (low or high).

The analysis of the primary objective involves knowledge of the treatment and then knowledge of the factors used in the minimisation which will be available for everyone from the randomisation.

AspECT

A phase III randomised study of Aspirin and Esomeprazole chemoprevention in Barrett's metaplasia

Funded by CR-UK, MRC, UHL and NCI

ISRCTN No.85156844

Secondary endpoints –adenocarcinoma, high grade dysplasia, death
As described for primary but for each event separately.

Secondary endpoints – clinical and molecular risk factors

Available for a varying number of patients

Secondary endpoint - cost effectiveness

This endpoint is not being analysed by CSM

Secondary endpoints - changes in molecular markers and genomics

This endpoint is not being analysed by CSM

Secondary endpoints – quality of life

It was not possible to collect this data across time so this analysis cannot be done

Secondary endpoints – biological risk factors for cardiac disease and aspirin resistance

Cardiac events fulfilling a seriousness criterion will be noted as SAE and this will be used as indicative of cardiac disease. Biological risk factors of hypercholesterol, family history, patient's history, hypertension, diabetes and smoking will be tabled to show availability of this data.

Secondary endpoints – gender effect

Gender data should be available on all from randomisation

Sensitivity analysis – presence of helicobacter will be defined as helicobacter seropositivity at any point in the trial.

Pathology – local pathology results will be used

7. Patient Groups for Analysis

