2.5.3 Exploratory sample size statement October 2008

Due to protocol amendments and an expected restriction on the number of patients to be recruited, an exploratory sample size is presented at the request of the Funders. Since the trial will recruit until end Dec 2008 in the UK and possibly until the end of June in Canada rather than to the number calculated in the original sample size, this calculation should be considered as a guide to the power and treatment effect size the trial should achieve.

This exploratory sample size is calculated as per the original sample size, but with

- Annual rate of conversion of 1% (allowing for the composite primary endpoint of all cause mortality and conversion to adenocarcinoma and conversion to high grade dysplasia.)

Justification: Using the National Statistics figures for 2005 based on the age and gender structure of the first 2046 patients recruited to AspECT gives a mortality rate in a year of 1.16%.

Using the UK Barrett's conversion rate to adenocarcinoma of at least 0.98% per year without treatment for 60% of the sample and 40% with a lower conversion rate of 0.66% (due to being

AspECT

A phase III randomised study of Aspirin and Esomeprazole chemoprevention in Barrett's metaplasia

Funded by CR-UK, MRC, UHL and NCI

ISRCTN No.85156844

female, have tongues of Barrett's metaplasia or only 1cm of Barrett's, or being <45 years old. Differing rates are not published for these patients so a rate of two thirds the UK conversion rate has been used) ie 0.85% conversion rate without treatment over the whole sample.

No good estimates of rates for conversion to high grade dysplasia for the UK could be found.

In this population, it is unlikely that the event rate for the composite primary endpoint in the control arm will be less than 1%.

- HR as in colorectal cancer
- No adjustment for compliance
- the follow-up increased to 10 years

Apart from limited recruitment and checking the event rate using the age/sex structure, no information or estimates from the current trial are used.

A total of 2224 patients (196 events) (approximately 556 in each intervention group) will allow us to detect a difference in conversion rates of 0.34% per year between low dose and high dose PPI and aspirin or no aspirin. This sample size was calculated using ARTMENU in STATA release 10.0 based on the following:

- Patients will be recruited over 3 years and followed up for a further 10 years

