2.7 Definition of Primary and Secondary Outcomes

Primary outcome is

- Time from randomisation date to conversion from Barrett's metaplasia to high grade dysplasia (event), or to adenocarcinoma of the oesophagus (event) or time to death from all causes (event) or time to last follow-up (no event)

I.e. the time is noted as the time from date of randomisation to high grade dysplasia, adenocarcinoma of the oesophagus or death, whichever is the earlier, with the survival time coded as an event. For patients who do not have one of these events of interest, the time from randomisation to date of last follow-up is calculated and the survival time coded as a censored event.

Secondary outcomes are

- Time from randomisation date to conversion from Barrett's metaplasia to high grade dysplasia (event) or time to last follow-up (no event) or event that precludes getting high grade dysplasia (for example death) (no event)
- Time from randomisation date to progression from Barrett's metaplasia to adenocarcinoma of the oesophagus (event) or time to last follow-up (no event) or event that precludes getting adenocarcinoma of the oesophagus (for example death) (no event)
- Time from randomisation date to death from all causes (event) or time to last follow-up (no event)
- Time from randomisation date to death from oesophageal cancer (event) or time to last follow-up (no event) or death from a cause other than oesophageal cancer (no event)
- Molecular markers to be identified at the end of the trial and used during analyses of collected blood and/or tissue samples
- Cost per oesophageal adenocarcinoma prevented

AspECT

A phase III randomised study of Aspirin and Esomeprazole chemoprevention in Barrett's metaplasia

Funded by CR-UK, MRC, UHL and NCI

ISRCTN No.85156844

- Cost per life year saved
- Molecular markers to be identified at the end of the trial and used with samples collected across time along with treatment information
- Cost per quality adjusted life saved
- Cardiac event from SAE (our best data on cardiac disease) and new tumours (a marker of aspirin resistance)
- For gender secondary, same outcome as for primary

AspECT

A phase III randomised study of Aspirin and Esomeprazole chemoprevention in Barrett's metaplasia

Funded by CR-UK, MRC, UHL and NCI

ISRCTN No.85156844

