8.8 Supporting information

The withdrawal rates from aspirin and PPI will be described as well as the dose of drug taken at time points throughout the trial.

9. Analysis to address secondary aims

There are many secondary aims so these will be described under each aim

- To assess whether intervention with aspirin results in decreased high-grade dysplasia, in decreased all cause mortality, in decreased adenocarcinoma oesophageal cancer incidence, and in decreased cause-specific mortality when each is considered separately

ANALYSIS: As for primary using the AFT model. As for primary using COX model for all cause mortality. For the COX model for high grade dysplasia, adenocarcinoma oesophageal cancer incidence and cause-specific mortality a competing risks approach will be used since there are expected to be many competing deaths for these endpoints.

For oesophageal cancer, as a sensitivity, the analysis will be rerun including all oesophageal cancers rather than just adenocarcinomas.

- To assess whether intervention with high dose PPI results in decreased high-grade dysplasia, in decreased all cause mortality, in decreased oesophageal cancer incidence and in decreased cause-specific mortality when each is considered separately

ANALYSIS: As for primary using the AFT model. As for primary using COX model for all cause mortality. For the COX model for high grade dysplasia,

AspECT

A phase III randomised study of Aspirin and Esomeprazole chemoprevention in Barrett's metaplasia

Funded by CR-UK, MRC, UHL and NCI

ISRCTN No.85156844

adenocarcinoma oesophageal cancer incidence and cause-specific mortality a competing risks approach will be used since there are expected to be many competing deaths for these endpoints.

For oesophageal cancer, as a sensitivity, the analysis will be rerun including all oesophageal cancers rather than just adenocarcinomas.

- Are there clinical and molecular risk factors than can be identified in BM for the development of BA?

ANALYSIS: Variables to be specified at the end of the trial. These variables of interest will be added to the accelerated failure time model with the event oesophageal adenocarcinoma and those found to be significant will be reported. The variables will also be considered in the competing risk COX approach.;

- What is the cost effectiveness of aspirin and/or PPI treatment in the prevention of BA?

The analysis will not be undertaken by CSM; to be analysed by [name]. Information from protocol:

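### The planned Kaplan-Meier curves for adenocarcinoma and high grade dysplasia censor deaths, so they modestly overstate conversion risk; cumulative incidence curves should replace them

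*SAP*

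**What the plan says.** SAP section 6.6 sets out how the primary endpoint will be described: "Kaplan-Meier curves will be drawn for all patients, then split by aspirin intervention and split by PPI dose (low or high"). For the secondary endpoints of adenocarcinoma, HGD and death it gives one line: "As described for primary but for each event separately". No exception is made for the curves.

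SAP section 2.7 defines what ends follow-up without an event. For HGD this includes an "event that precludes getting high grade dysplasia (for example death) (no event"); for adenocarcinoma, an "event that precludes getting adenocarcinoma of the oesophagus (for example death) (no event"). Death from oesophageal cancer is defined in the same way, with death from any other cause coded as no event.

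SAP section 9 gives the comparative analysis of these endpoints. The AFT analysis is "As for primary using the AFT model". For the Cox model of HGD, adenocarcinoma and cause-specific mortality, "a competing risks approach will be used since there are expected to be many competing deaths for these endpoints". The approach is not named. Neither document specifies a cumulative incidence function.

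**The concern.** When death is censored, one minus Kaplan-Meier does not estimate the share of patients who convert. At best, if death and conversion are independent, it estimates the share who would convert if nobody died first. Wherever deaths occur it lies above the actual cumulative incidence, and the gap grows with follow-up.

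The SAP recognises the problem for one model of these endpoints but not for the plots of the same endpoints. Separate effects on HGD and adenocarcinoma are stated secondary objectives, and the SAP governs the main paper. A reader who takes an absolute conversion risk from the published curves would take one that is too high.

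**Working it through.** **Inputs**
- Adenocarcinoma without treatment: "0.85% conversion rate without treatment over the whole sample" (SAP section 2.5.3). It reproduces from the two rates given there: 0.6 × 0.98 + 0.4 × 0.66 = 0.852.
- Mortality: 1.16% a year for the age and sex structure of the first 2046 patients (same section).
- Horizon: 8 years, or 10 for those who re-consented (Protocol section 5.2).
- HGD rate: SAP section 2.5.3 says that no good UK estimate was found. I assume 0.5% a year.

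**Formulas**, with constant hazards *l* (event of interest) and *m* (competing event):
- One minus Kaplan-Meier, deaths censored: 1 − exp(−*l*t).
- Cumulative incidence: *l*/(*l*+*m*) × [1 − exp(−(*l*+*m*)t)].

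**Adenocarcinoma**, *l* = 0.0085, *m* = 0.0116:
- 8 years: 1 − exp(−0.068) = 6.57%, against 0.4229 × [1 − exp(−0.1608)] = 6.28%. Excess 0.29 points, 4.7% relative.
- 10 years: 1 − exp(−0.085) = 8.15%, against 0.4229 × [1 − exp(−0.201)] = 7.70%. Excess 0.45 points, 5.8% relative.

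At these rates deaths outnumber adenocarcinomas. Over 10 years in 2513 patients, ignoring HGD and losses, about 264 would die first (2513 × 0.5771 × 0.1821) and about 194 would convert first (2513 × 0.0770).

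**Sensitivity at 10 years**

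| Adenocarcinoma rate | Mortality | 1 − KM | Cumulative incidence | Relative excess |
|---|---|---|---|---|
| 0.66% | 1.16% | 6.39% | 6.03% | 5.8% |
| 1.39% | 1.16% | 12.98% | 12.27% | 5.8% |
| 0.85% | 0.58% (assumed) | 8.15% | 7.92% | 2.9% |
| 0.85% | 1.16%, rising 10% a year (assumed) | 8.15% | 7.52% | 8.4% |
| 0.85% | 2.32% (assumed) | 8.15% | 7.28% | 11.9% |

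The 0.66% is the lower-risk rate in SAP section 2.5.3, and the 1.39% is the upper confidence limit in section 2.5.1.

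**HGD at 10 years**, assumed *l* = 0.005. One minus Kaplan-Meier is 1 − exp(−0.05) = 4.88%.
- Death alone competing (*m* = 0.0116): 0.3012 × [1 − exp(−0.166)] = 4.61%. Excess 5.9% relative.
- Death and every adenocarcinoma competing (*m* = 0.0116 + 0.0085 = 0.0201): 0.1992 × [1 − exp(−0.251)] = 4.42%. Excess about 10% relative. This is an upper bound for these rates, because it supposes that no adenocarcinoma is preceded by HGD.

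**Difference between arms at 10 years.** I apply the hazard ratio of 1.5 from SAP section 2.5.3 to adenocarcinoma, so the treated rate is 0.85/1.5 = 0.567% a year.
- One minus Kaplan-Meier: 8.15 − 5.51 = 2.64 points.
- Cumulative incidence, equal mortality: 7.70 − 5.20 = 2.50 points.
- Cumulative incidence, if treatment also divides mortality by 1.5: 7.70 − 5.30 = 2.40 points.

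**Sample size.** Freedman's formula at a ratio of 1.5, 80% power and two-sided 5% gives 196.2 events, in line with the SAP's 196. That figure concerns the composite, in which death is an event, so it does not change.

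**The case against.** The strongest reply is that this is a small presentational matter. Section 6.6 describes available data, and the inference is in section 9. The SAP nowhere says that one minus Kaplan-Meier will be reported as an absolute risk. At 8 years, the basic follow-up, the excess is 0.29 points. With about 1,250 patients per arm, a simple binomial 95% half-width at 10 years is about 1.5 points (1.96 × √(0.0815 × 0.9185/1250)), roughly three times the 0.45-point bias. Censoring deaths in an AFT model is also a legitimate cause-specific analysis. All of this stands and limits the size of the point. It does not remove it: the curves are planned, the bias has one direction, and more patients would not reduce it.

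A reader might infer more than the documents support:
- *That the cost-effectiveness results will be biased.* Protocol section 14 and SAP section 9 describe a state transition model that already allows for competing death, and neither says that it will draw on these curves.
- *That the error is much larger in older patients.* It would grow with mortality, but no curve by age is planned and the documents give no mortality rate for an older group.
- *That the curves will conflict with the Cox results.* Section 9 does not say whether its approach is cause-specific or Fine-Gray. A cause-specific Cox model also censors deaths, so a conflict cannot be shown.
- *That the treatment comparison is materially distorted.* The figures above show a shift of 0.14 points with equal mortality, and 0.24 points if treatment also lowers mortality.
- *That a misleading curve is planned for oesophageal cancer death.* Section 6.6 lists adenocarcinoma, HGD and death, and specifies no such curve.

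**Conclusion.** The point holds at modest size. Following SAP sections 6.6 and 2.7 as written gives adenocarcinoma and HGD curves whose complement overstates the proportion converting, although section 9 acknowledges many competing deaths. For adenocarcinoma the relative excess is about 5% at 8 years and 6% at 10, on the documents' rates and constant hazards; higher or rising mortality would enlarge it. For HGD the direction is certain, but the size (about 6% to 10% relative at 10 years) rests on an assumed rate and on how many adenocarcinomas arise without prior HGD. The primary composite and all-cause mortality are unaffected, because death is an event in both.

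**What to change.** In SAP section 6.6:
- Draw Aalen-Johansen cumulative incidence curves, overall and by each randomised comparison, for adenocarcinoma (death competing) and for HGD (death, and adenocarcinoma without prior HGD, competing).
- Do the same for oesophageal cancer death, with death from other causes competing, if a curve is drawn.
- Keep Kaplan-Meier for the composite and all-cause death.

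In SAP section 9:
- State that AFT results that censor deaths are cause-specific.
- Name the competing-risks Cox method.

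The curves cost one sentence in the SAP and a standard software command; the labels in section 9 need a further line. No new data are needed.

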# 7 SAMPLES FOR LABORATORY ANALYSIS

## 7.1 Samples to be analysed in local Trust's laboratories

### ***Pathology***

Biopsy samples are collected from patients participating in the trial. Patients were endoscoped at baseline (the endoscopy prior to randomisation is defined as the baseline visit for patients recruited retrospectively) and thereafter, will be endoscoped at approximately 2 yearly intervals from the date of randomisation (+/- 3 months either side). At each endoscopy any macroscopic abnormality of the Barrett's metaplasia will be biopsied for formalin fixation and histological assessment for dysplasia.

The routine diagnostic pathology samples taken at endoscopy will be labelled, processed and reported according to local hospital protocols.

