### 21.3 Quality Monitoring Committees

There are specific central Quality Monitoring Committees (QMCs) for endoscopy (coordinator [name]), pathology (coordinators [name]/[name]), physiology (coordinator [name]), molecular biology (coordinator [name]) and health economics (coordinator [name]).

Endoscopy QMC: During the trial, visits will be undertaken by the trial and endoscopy coordinator (or their deputies) to sites where concerns about endoscopy rise.

Pathology QMC: this group will jointly assess the suitability of the local pathology resources. A proportion of all normal cases (approximately 10%) will have their slides reviewed centrally. In addition, all dysplastic and neoplastic specimens will also be reviewed centrally by one of two panels of five expert pathologists, who will return a consensus score. They will ensure that all criteria for the histological diagnosis for metaplasia, dysplasia and cancer are met. Any normal cases found to be dysplastic or neoplastic on review will be put into the abnormal panel review process. All cases will have 'research paraffin tissue blocks' as well as fresh tissue where available. The central pathology panels will report compliance to the TMG. The pathology coordinator will submit the final pathology review results to the local site PI.

Molecular biology QMC: this group will assess the suitability of the local resources for collecting additional blocks for pathology as well as tissue storage. All patients had blood samples collected at baseline and 4-6 years after randomisation. They will have blood sample taken 8 years after randomisation. In addition, all patients will have at

least one histological block from each case sent to the Trial Laboratory. Furthermore, where available, fresh tissue samples can be stored locally and sent in batches to the AspECT Trial Laboratory. The co-ordinators will ensure that all assays are carried out to standard operating procedures. The conversion to cancer will be assessed from baseline to the end of the study. All individuals will be assessed for trial inclusion/exclusion criteria and after informed consent they will have a baseline blood sample for helicobacter serology, PBMC isolation, storage of blood DNA for genetic assessment and baseline biochemistry.

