2.6.2 Blinding

After randomisation, both the patient and the treating doctor knows what treatment the patient is receiving. There is no blinding of treatments. (The cost of placebo drugs was prohibitively expensive.)

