0.8	19 th Sep 2008	Updated to version 10 of the protocol Sample size section tidied, now giving only the original and the guidance for 2500 patients
0.81	3 rd Oct 2008	Contents page corrected Sample size exploratory calculation changed. Minor changes of text for clarity.
0.82	14 th Oct2008	Typo corrected
0.83	6 th Jan 2009	Put in analysis for third secondary aim and for last secondary aim
1.0	29Jul2013	Updated to version 10 of protocol All contact details in section1 updated Secondary endpoint split into those within the study and those investigated as substudies Oesophagitis secondary endpoint added Number of events added to sample size information Definition of oesophageal cancer secondary endpoint added Interim analysis, emphasised no plans to disseminate Clarification that trial uses local pathology Describe withdrawal rates Added several sensitivity analyses Added exploratory of dose/time effect Added specific look at renal impairment Express number of major bleeds per 1000 years
1.1	20Aug2013	Changed interim analysis p value to 0.001 as standard
1.2	25Jan2014	Made notes for next version in red on page 1
1.21	6Apr2017	Updated contacts, protocol number and footer
1.22	20Apr2017	Updated to protocol 12
1.31	12Jun2017	Updated after conversation with PI
1.32		Minor edits – each typo corrected as it is seen
1.33		Minor edits
1.34		Minor edits
1.35		Minor edits
1.36		Minor edits
1.37		Minor edits
1.38	15Aug2017	[name]'s comments added, explicit statement made about Canada data
2.0	24Aug2017	All changes accepted and comments deleted

AspECT

A phase III randomised study of Aspirin and Esomeprazole chemoprevention in Barrett's metaplasia

Funded by CR-UK, MRC, UHL and NCI

ISRCTN No.85156844

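### No analysis uses the planned five-expert central pathology consensus to test the HGD and adenocarcinoma events of this open-label trial

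*SAP*

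**What the plan says.** **Endpoint source.** The primary outcome is time to the first of HGD, oesophageal adenocarcinoma or death from any cause (protocol 13.1, SAP 2.7). HGD and adenocarcinoma are also separate secondary outcomes. Protocol 7.1 has diagnostic biopsies "labelled, processed and reported according to local hospital protocols". SAP 6.6 says that "local pathology results will be used". The SAP document history for version 1.0 records "Clarification that trial uses local pathology", so this was deliberate. SAP Appendix 2 takes the HGD and adenocarcinoma dates from the endoscopy or follow-up form.

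**Blinding.** SAP 2.6.2 says "There is no blinding of treatments" and that "both the patient and the treating doctor knows what treatment the patient is receiving".

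**Central review.** Under protocol 21.3, "all dysplastic and neoplastic specimens will also be reviewed centrally by one of two panels of five expert pathologists", "who will return a consensus score". For the rest, "A proportion of all normal cases (approximately 10%) will have their slides reviewed centrally", and any normal case found abnormal then goes to the panel process. The panels are to see that diagnostic criteria are met and to report compliance to the Trial Management Group. The pathology coordinator sends final results to the site investigator.

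**Other sources.** Deaths and many adenocarcinomas can also be found through NHS Digital flagging (SAP 6.3, 6.6). SAP 6.6 accepts that HGD will be under-represented among patients lost to follow-up.

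**The concern.** An expert consensus read is planned for the specimens on which most non-fatal events depend, yet it enters no analysis. Two kinds of error could pass untested. Local HGD calls that an expert panel would not confirm, if equally common in both arms, pull the treatment ratio towards 1. Calls made more readily in one arm, which open treatment makes possible, bias the ratio in either direction. The design has about 80% power, so there is little room for dilution.

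The omission stands out against the checks that the SAP does contain. Its sections 7 and 8.6 re-run the models because Barrett's length was wrong at randomisation for 60 patients, which is an error in a covariate. SAP section 5 follows up resections and ablations that have no logged progression, which looks for missed events. No planned analysis examines over-called events.

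**Working it through.** **1. Is the central read used anywhere?** Protocol section 14 specifies logrank, AFT and Cox analyses, a per-protocol analysis and an interaction check. SAP 8.6 lists per-protocol, interaction, helicobacter, gender, NSAID and COX-inhibitor use, actual Barrett's length, all oesophageal cancers, and two censoring rules. SAP section 9 repeats the primary methods for each component, with competing risks in the Cox models. None refers to the central consensus, and no local-by-central agreement table is planned.

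**2. The plan's own event target.** Freedman's formula with ratio 1.5, two-sided 5% and 80% power gives (1.960 + 0.842)² × (2.5/0.5)² = 7.849 × 25 = 196.2. This reproduces the 196 events in SAP 2.5.3. Schoenfeld's formula gives 191.

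**3. Equal over-calling in both arms (illustration).** From the documents: a ratio of 1.5, which splits true events 0.6 to 0.4 between control and treated, and 200 events (protocol 14.1). Assumed: 40 to 80 of the 200 events are HGD, and 20% to 40% of local HGD would not be confirmed. That gives 0.2 × 40 = 8 to 0.4 × 80 = 32 false events.

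Apparent ratio = (0.6T + F/2) / (0.4T + F/2), with T true and F false events.

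- HGD alone, 20% false: 0.58/0.42 = 1.38.
- HGD alone, 40% false: 0.56/0.44 = 1.27.
- Composite, 8 false: (115.2 + 4)/(76.8 + 4) = 119.2/80.8 = 1.475.
- Composite, 32 false: (100.8 + 16)/(67.2 + 16) = 116.8/83.2 = 1.404.

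Power is Φ(√(200/4) × ln ratio − 1.96). It is about 82% at 1.5, 78.5% at 1.475 and 67% at 1.404.

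**4. Unequal over-calling with no true effect (illustration).** Take 98 events per arm. The HGD or cancer share is set at 0.42, from the SAP 2.5.3 rates: 0.85/(0.85 + 1.16), with HGD not counted because no UK rate is given. If one arm has k extra HGD or cancer calls, its events become 98 × (1 + 0.42k).

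- k = 10%: ratio 0.96, two-sided type I error about 6%.
- k = 20%: 98/106.2 = 0.92, about 9%.
- k = 30%: ratio 0.89, about 14%.

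**5. What the central reads could correct.** The panels see all dysplastic specimens. That includes local low grade dysplasia, so they can upgrade to HGD as well as downgrade from it. They see only about 10% of normal cases, so missed events among normals are corrected only in part. A change between HGD and adenocarcinoma affects the secondaries but usually not the composite. The boundary between low and high grade dysplasia affects both.

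**6. A complication for any re-analysis.** Under protocol 6.4, a local HGD diagnosis leads to withdrawal from trial medication and may be followed by ablation or resection. If the panel does not confirm it, the patient returns to the risk set with treatment already changed by the local call.

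**The case against.** Local pathology was chosen on purpose in a pragmatic trial, and it is the diagnosis on which patients are managed. That stands, and it is why local reads should stay primary. An unlisted analysis could still be run as exploratory under SAP section 10, but the rules in steps 5 and 6 would then be set after the data were seen.

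Several stronger readings are tempting, and the documents do not support them:

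- *The central reads already exist for every event that could be overturned.* Protocol 21.3 describes a plan. Completion is not documented, and nothing says that specimens from cancers found through NHS Digital reach a panel.
- *The whole endpoint rests only on local pathology.* Death does not depend on it, and cancer has a second source. The point applies in full only to HGD.
- *The plan has no check.* Central review is itself quality assurance. What is absent is an analysis that uses its result.
- *Knowledge of treatment biased the local reads.* Only the patient and the treating doctor are said to know the allocation. The documents do not say whether local pathologists or the panels know it, so a central-read analysis cannot be assumed free of the same bias.
- *A central-read analysis involves no trade-off.* Step 6 shows that it does.

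The dilution figures are also open to challenge. The formula treats each false HGD as a pure extra event, although some of those patients would later have a true event, so it tends to overstate dilution. At the mild end the composite ratio moves only from 1.50 to 1.475.

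**Conclusion.** The omission is clear from the documents: a consensus read is planned for all dysplastic and neoplastic specimens, local reads define the events, and no analysis uses the consensus. A pre-specified sensitivity analysis should be added.

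The size and direction of any effect are not known. Composite ratios of 1.48 to 1.40, HGD-only ratios of 1.38 to 1.27 and type I error of 6% to 14% are illustrations. They rest on assumed HGD counts, non-confirmation rates and extra-call rates that the documents do not give. SAP 2.5.3 itself says that no good UK estimate of the HGD rate could be found. The figures show that the check is worth making, not that the trial result is wrong. Because local reads stay primary, the check would not restore power lost to dilution. No sample-size figure needs to change.

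**What to change.** Keep local pathology as primary. Add to SAP 8.6 and section 9:

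- **Analysis.** Repeat both co-primary analyses and the HGD and adenocarcinoma secondaries with these events classified by central consensus where a central read is available, dated at the original sample.
- **Upgrades and downgrades.** Count both, for example local low grade dysplasia read centrally as HGD. Where there is no central read, keep the local or registry classification.
- **Unconfirmed local HGD.** Report the analysis twice: with follow-up continued, and with censoring at the local HGD date. Neither is clean, because the local call changes later treatment, so both are needed.
- **Agreement.** Tabulate local against central classification by randomised arm, with the number of specimens that have no central read.
- **Statements.** Say whether the panels were blinded to allocation, and whether site records were revised after central review. If they were, define which result counts as local.

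The cost is a little more programming and reporting, with no reads beyond those already planned. The remaining limit is that missed events are only partly corrected, because about 10% of normal cases are reviewed.
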